Given existing RCTs,(117-123), we expect MT and SMT to produce similar overall outcomes. As a comparative mechanisms study, analyses will focus primarily on documenting and characterizing mechanism effects. Note that all mechanism and outcome measures will be completed by all participants in both treatments at each assessment point, thus allowing us to test the degree to which mechanisms not specific to a treatment change and account for outcomes. To support the existence of a specific mechanism, analyses would reveal that: 1) putative specific mechanisms (i.e., mindfulness in MT, spinal stiffness in SMT) will show the largest pre-post changes in the relevant treatment condition (e.g., MT mindfulness changes > SMT mindfulness changes); 2) substantial changes in the mechanism will precede and predict substantial subsequent changes in outcomes only in the relevant treatment (e.g., mindfulness changes predict pain interference changes only in MT).

We will also take full advantage of this design and evaluate effects of mechanisms beyond pre- to post-treatment changes in outcomes. To our knowledge, no methodologically rigorous published study has yet examined effects of mechanisms on pre-post changes in concert with effects of mechanisms on maintenance or expansion of gains during follow-up. It may be that the true value of a mechanism may only be revealed through its effects on sustained gains out to 6-mos after treatment. Thus, mechanisms that do not show strong links with pre-post outcome changes may emerge as delayed predictors of 3- and 6-mos outcomes. Only by separating immediate pre-post mechanism effects from longer-term post-treatment mechanism effects can we build on current knowledge regarding the extended value

of C/I interventions for chronic pain.

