6.2.4 Treatment Visits

Treatment Sessions 1-8 (Visits 4, 5, 6, 7, 8, 9, 10, 11)

- MT and SMT treatments (as assigned) will be conducted during these visits.
- Assessment of spinal stiffness pre- and post-session as described above.
- Patient engagement in session will be rated by therapist.
- Assessment of any adverse events.

Assessed via phone call by RA within 48 hours of session or online via REDCap by the patient:

- Pain interference (primary outcome), pain intensity, negative affect (anger, anxiety, depression), physical function, sleep disturbance and social support will be assessed via designated PROMIS measures.
- Pain catastrophizing will be assessed with the Pain Catastrophizing Scale.
- Mindfulness will be assessed with the Five Facets of Mindfulness Questionnaire (short form), and the Multidimensional Assessment of Interoceptive Awareness (short form).
- Self-efficacy will be assessed with the Pain Self-Efficacy Questionnaire.
- Bothersome pain and attitudes on changing pain (Pain Stages of Change Questionnaire) will also be assessed.

Treatment sessions 3 and 6

In addition to the measures above, the following measures will be given:

- The Working Alliance Inventory – short form, and the Scale to Assess Therapeutic Relationships – Patient Version will be administered in-person.
- The Reaction to Treatment Questionnaire will be administered in-person.

Post-Treatment Lab Sessions (Visits 12, 13)

- A urine sample will be collected and tested for opioids (using a rapid single panel opioid screening test) and pregnancy (females only – using an analog pregnancy test).
- Post-treatment endogenous opioid function and conditioned pain modulation will be assessed via the QST procedures described in Section 5.2.
- To enable potential future assessment of treatment-related changes in relevant biomarkers, a 4mL sample of whole blood will be drawn from the cannula placed for drug administration into a tube with EDTA prior to beginning laboratory pain or drug administration procedures in both laboratory sessions. Within 10 minutes of collection, samples will be centrifuged for 10 minutes at 3500rpm and 4°C. Plasma will then be pipetted into microcentrifuge tubes (0.5mL aliquots) and stored at -80°C until assayed.
- McGill Pain Questionnaire administered during the QST procedures.
- Evoked pain intensity and unpleasantness and naloxone side effects will be assessed.
- Assessment of any adverse events.

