In the absence of interactions, we will use linear mixed effects regression models to test the degree to which changes in non-specific and specific mechanisms account for unique and shared variance in pre-post outcome changes. More specifically, 0-order correlations among mechanism and outcome pre-post change scores will reveal “candidate” mechanisms (i.e., those with significant associations with pre-post outcome changes). We will use a series of hierarchical regressions to examine the degree to which ostensibly different mechanisms account for shared or unique variance in outcome changes. Such analyses will allow us to identify common areas of mechanism overlap (e.g., changes in self-efficacy and pain catastrophizing accounting for much shared variance in pain changes), and mechanism uniqueness (e.g., changes in spinal stiffness accounting for significant unique variance in pain changes even with other mechanism changes controlled).

Aim 4: Address competing causation pathways.

First, we will use an approach and techniques that we have used in previous publications [eg, [name], J.W., Nielson, W.R., Jensen, M.P., Heapy, A., Czlapinski, R., & Kerns, R.D. (2015). Specific and general therapeutic mechanisms in cognitive-behavioral treatment of chronic pain. *Journal of Consulting and Clinical Psychology*. 83, 1-11. PMID: 24979313]. Namely, we will test lagged and cross-

lagged effects using pre- to mid-treatment and mid- to post-treatment epochs. Given that endogenous opioid functioning will be assessed only at pre-and post-treatment, and given that the working alliance and subject expectations for benefit will be assessed only at 3- and 6-weeks, this approach will allow to examine comparable effects across all our specific and non-specific mechanisms. Residual change scores for all mechanism and outcome variables will be computed by regressing mid-treatment on pre-treatment values (i.e., a pre-mid residual change score), and regressing post-treatment on mid-treatment values (i.e., mid-post residual change score). For lagged relationships, regressions will be performed to identify the unique effect of pre-mid mechanism changes on mid-post outcome changes. This will require statistically controlling for the path from pre-mid mechanism change to mid-post mechanism change and pre-mid outcome change to mid-post outcome change. See Figure 1 and 2 below. The red line is the target lagged effect. The two blue lines are the paths to be controlled.

Figure 1

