[figure not shown]
[figure not shown]

Figure 2

For cross-lagged effects, the procedure will be inverted. Namely, we will test whether pre-mid changes in outcomes predict mid-post changes in mechanisms. Significant lagged effects paired with non-significant cross-lagged effects will add support to the notion that early-treatment changes in putative mechanisms influenced later-treatment changes in outcomes. In general, we expect that pre-mid changes in mindfulness and spinal stiffness will predict mid-post changes in pain interference (and other outcomes), but the inverse will not be the case.

Second, we will take a more fine-grained HLM approach using the weekly data. We will test whether: a) previous week levels of specific (e.g., mindfulness, spinal stiffness) and nonspecific mechanisms (e.g. self-efficacy) predict previous week to next week changes in outcomes; b) these relationships depend on time in treatment (i.e. quadratic trends could emerge indicating that early- vs late-treatment effects are distinct); c) whether the inverse relationships (i.e. outcomes predicting mechanisms) are also significant; d) whether patterns of lagged effects are different between MT and SMT. In general, we expect that previous week levels in mechanisms will predict previous week to current week changes in outcomes, and that the strength of these relationships will be strongest from Week 3 to Week 6 (when specific mechanisms have improved sufficiently to best affect improvements in outcomes).

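### The weekly lagged test in Aim 4 is stated as previous-week mechanism level predicting outcome change, without the previous week's outcome and without separating within-person from between-person variation

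*Protocol*

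**What the plan says.** Section 9.6 gives Aim 4 two approaches.

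- **Pre-mid and mid-post epochs.** "Residual change scores for all mechanism and outcome variables will be computed by regressing mid-treatment on pre-treatment values", and likewise for post on mid. The lagged regressions must also control the prior mechanism path and the prior outcome path.
- **Weekly hierarchical models.** These ask whether "previous week levels of specific (e.g., mindfulness, spinal stiffness) and nonspecific mechanisms (e.g. self-efficacy) predict previous week to next week changes in outcomes". The expected result repeats the form: "we expect that previous week levels in mechanisms will predict previous week to current week changes in outcomes". The interval thus ends at the next week in one sentence and at the current week in the other. The reverse direction is to be tested too: "whether the inverse relationships (i.e. outcomes predicting mechanisms) are also significant". Dependence on time in treatment and differences between treatments are also named.

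The weekly text does not mention the previous week's outcome as a covariate, person-mean centring, or whether change is raw or residual. Section 9.6 uses both kinds elsewhere: Aim 3 works with plain change scores ("0-order correlations among mechanism and outcome pre-post change scores will reveal").

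On measurement, section 6.2.4 has the self-report mechanisms and outcomes collected together each week: "Assessed via phone call by RA within 48 hours of session or online via REDCap by the patient". Stiffness is measured by device at the session: "Assessment of spinal stiffness pre- and post-session as described above".

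**The concern.** A raw change score contains the previous week's outcome with a negative sign. If the mechanism and the outcome move together in the same week, the previous week's mechanism is correlated with that component whether or not any lagged effect exists. Regressing change on the mechanism level alone then mixes the lag with ordinary week-to-week reversion of the outcome. For a helpful mechanism (more self-efficacy, less pain interference) the reversion term has the opposite sign to the lag being sought. The inverse test has the same structure, so comparing the two directions is affected as well.

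Self-efficacy, catastrophizing, mindfulness and pain interference share one weekly survey, so a same-week correlation of zero is unlikely for them. For spinal stiffness the problem arises only if stiffness and outcome co-vary within persons.

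At stake is the second of two approaches to the final secondary objective. Section 3 gives lagged effects as a reason for assessing so often, and the weekly model is the Aim 4 approach that uses that resolution.

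**Working it through.** **Inputs.** The protocol gives no power or effect size for Aim 4, so there is no figure to reproduce. From the protocol: 240 analysable participants (section 9.2), 8 weekly assessments (section 6.2.4), and two-sided 5% (section 9.6, stated for Aims 1–2 and assumed here). Not in the protocol, hence assumed and varied: φ, r, ICC (taken equal for mechanism and outcome) and the true lag b. The data model is a stationary within-person process plus stable person effects.

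**Step 1: raw change.** Within persons, with unit variances, Y(t) = φ·Y(t−1) + b·M(t−1) + e. Then

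Y(t) − Y(t−1) = b·M(t−1) − (1−φ)·Y(t−1) + e.

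Stable outcome differences cancel. The covariance with M(t−1) is b − (1−φ)·r, and the variance of the mechanism level is 1/(1−ICC). So

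slope = (1−ICC)·[b − (1−φ)·r].

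There is no bias from the second term if r=0 or φ=1. A true lag in the direction of r takes the wrong sign when it is smaller than (1−φ)·|r|: 0.1×0.1 = 0.01, 0.3×0.2 = 0.06, or 0.5×0.3 = 0.15.

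**Step 2: numbers, ICC 0.5.** Simulated slopes match the formula. Rejection is given for a random-intercept model / for cluster-robust standard errors.

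| φ | r | true b | slope | result |
|---|---|---|---|---|
| 0.5 | −0.3 | 0 | 0.5×0.15 = +0.075 | wrong-sign rejection 100% / 100% |
| 0.7 | −0.2 | 0 | 0.5×0.06 = +0.030 | wrong-sign rejection 65% / 84% |
| 0.5 | −0.1 | 0 | 0.5×0.05 = +0.025 | wrong-sign rejection 24% / 53% |
| 0.9 | −0.1 | 0 | 0.5×0.01 = +0.005 | wrong-sign rejection 7% / 12% |
| 0.5 | −0.3 | −0.10 | 0.5×(−0.10+0.15) = +0.025 | wrong-sign rejection 25% / 55% |
| 0.5 | −0.1 | −0.10 | 0.5×(−0.10+0.05) = −0.025 | found in 25% / 54% |
| 0.9 | −0.1 | −0.10 | 0.5×(−0.10+0.01) = −0.045 | found in 100% |

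Moving ICC from 0.2 to 0.7, with no true lag, changes the random-intercept rejection from 8% to 5% (φ 0.9, r −0.1), 44% to 10% (0.5, −0.1) and 100% to 99% (0.5, −0.3).

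**Step 3: residual change.** Add Y(t−1) but no person split, with no true lag. With equal within- and between-person correlations, error is about nominal. When they differ, false effects in the expected direction (nominal 2.5%, cluster-robust) are:

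| r within, between | φ 0.5 | φ 0.7 | φ 0.9 |
|---|---|---|---|
| −0.2, −0.3 | 12% | 10% | 7% |
| −0.1, −0.2 | 13% | 10% | 5% |
| 0, −0.2 | 39% | 23% | 11% |
| 0, −0.4 (extreme) | 91% | 74% | 32% |

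**Step 4: centring alone is not a repair.** Person-mean centring the mechanism, still with raw change and no Y(t−1), raises the null slope from +0.025 to +0.073 (φ 0.5, r −0.1) and from +0.005 to +0.045 (φ 0.9, r −0.1).

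**Step 5: differing trajectories.** Let people differ in linear improvement (SD of total change equal to 1 within-person SD, slopes correlated −0.5). Wrong-sign rejection for raw change falls from 52% to 10% at φ 0.5, r −0.1, but stays at 99% at φ 0.5, r −0.3. Under the same trajectories, person fixed effects with the lagged outcome give 8% to 39% false effects in the expected direction over φ 0.5–0.9 and r −0.1 to −0.3. With slopes half that size the excess is small.

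**Step 6: which repair.** With only a reverse effect of −0.10 and r −0.3, fixed effects falsely reject in 16%, 28% and 52% (φ 0.5, 0.7, 0.9). A random-intercept cross-lagged model rejects in 4.5% (φ 0.5) and 5.0% (φ 0.7), and in 5.8% with no effect either way (φ 0.5). For a true lag of −0.10 at φ 0.5 its mean estimate is −0.100, with rejection in 94%.

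**The case against.** The best defence is that the weekly paragraph lists research questions, not a model. It prints no equation, unlike Aims 1 and 2, and it rules out neither a lagged outcome nor centring. Such details often go into a statistical analysis plan, which is not at hand. The nearest text, in the same aim, defines residual change. On that reading the sign reversal largely goes away.

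Much of this stands. A reader might infer that the protocol prescribes raw change and that the weekly results will therefore have the wrong sign. The documents do not support that, because the kind of change is left open. What remains is that the predictor and response are stated twice in a form that, followed literally, gives a biased lag. The controls set out for the epochs are not carried over, and Aim 3 shows that change in this section need not mean residual change. Even the residual reading leaves the person-level confounding in Step 3.

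A reader might also infer that the protocol's test for a specific mechanism is undermined. Section 3 requires that "substantial changes in the mechanism will precede and predict substantial subsequent changes in outcomes only in the relevant treatment". That is change predicting change, and the controlled pre-mid/mid-post analysis is the closer match to it.

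The objection that removing stable person differences is not sufficient when trajectories differ is also correct (Step 5), and it narrows the remedy.

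**Conclusion.** The point holds as a defect in the stated form of the weekly Aim 4 test and, by extension, its inverse. Under raw change, a true lag is attenuated, masked or reversed unless φ is near 1 or r near 0. Under residual change, bias is small if within- and between-person correlations agree, and runs in the expected direction if the between-person correlation is the stronger.

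The size cannot be fixed from the documents. Over the values tried, wrong-sign rejection under raw change with no true lag runs from 5% to 100%. Large, correlated differences in improvement trajectories reduce it, in some settings to little. The algebra is certain given the model; which setting applies is not.

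The scope is limited to one of two approaches to the last secondary objective. The primary outcome, the sample size, Aims 1–3 and the epoch analysis are not touched. It merits correction because the change is to wording and no new data are needed.

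**What to change.** Restate the weekly model in section 9.6 as current-week outcome on previous-week outcome and previous-week mechanism. Add week effects and separate within-person from between-person effects. Give the mirror model for the inverse direction, keep the time and treatment interactions, and use one wording for the interval.

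Implement the separation with a model that estimates the person effects jointly with the lag, such as a random-intercept cross-lagged model. Add a sensitivity analysis allowing person-specific linear trends. Do not rely on person fixed effects alone, given their short-series bias under a reverse effect and their false positives when trajectories differ. The cross-lagged model was itself checked only at r −0.3 and φ 0.5–0.7, without trends or interactions, so the sensitivity analysis is needed.

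The cost is some extra modelling and somewhat lower power, because between-person information no longer feeds the lag. At φ 0.5, r −0.3, power is 94–97% for a lag of −0.10 and about 50% for −0.05.

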10. DATA COLLECTION AND QUALITY ASSURANCE

10.1 Data Collection Forms

All data will be collected in REDCap; weekly surveys will be done over the phone with the RA reading items to subjects and entering their responses directly into REDCap or completed online in REDCap directly by the subject. As part of the end of the month data check RAs will review the REDCap to ensure that all forms that should be marked as completed are and also that no records were erroneously marked as completed.

Protocol compliance and data quality review will be ongoing with daily meetings between the PIs and research assistants. All data collection will be reviewed within days of collection so that the opportunity for feedback to research staff or the participants can occur. Additionally, all study materials and data are reviewed for accuracy and completeness by a trained research assistant within days of each subject completing the study to reduce the possibility of missing data.

The research assistants will be the primary collectors of data, and will refer questions to the PIs as they arise. All data entry will be double checked by the PIs, or a separate trained research assistant. Participants will complete weekly questionnaires via telephone calls with RAs or online via REDCap. Several aspects of the study procedures will be designed to minimize risks to confidentiality. Data will be coded and transferred to a computer database for later analysis. All paper and computer records, will be identified only by subject ID number rather than subject name to help ensure confidentiality. All subject records will be maintained in filing cabinets in the locked labs of the PIs, and will be accessible only to the PIs and research assistants. Hard copies of the data will be maintained for 6 years after the study, after which they will be destroyed. Computer data files (without subject IDs) will be maintained by the site PIs for future use. Consents and any other forms with identifiable subject information will be maintained in a separate locked file from the actual study data files, which will be identified only by subject number. All subjects will be informed regarding how HIPAA requirements may impact on their study records, and will sign a notification regarding this issue. All published data will be reported in a manner in which individual data for specific subjects are not identifiable.

No data will be directly recorded onto a case report form.

10.2 Data Management

We have extensive experience with studies of this type, and plan to employ the same types of strategies in the proposed project to address all of these issues. Our intention is to use REDCap (developed at Vanderbilt where Co-PI [name] is located) for data entry and data storage, a system that it is widely used, highly reliable, and secure. Data will be coded on paper and transferred to a computer database for later analysis. All paper and computer records, and digital video-recordings of sessions will be identified only by subject ID number rather than subject name to help insure confidentiality. All subject records will be maintained in filing cabinets in the locked offices of the PIs or designees, and will be accessible only to the PIs, co-I's and designees. Hard copies of the data will be maintained for 6 years after the study (including the audiotapes/videotapes), after which they will be destroyed. Computer data files (without subject IDs) will be maintained by the site PIs for future use. All

paper and computer data records will be identified by a subject number assigned solely for use in this study rather than by name to help insure confidentiality. The individual subjects associated with each subject number will be known only to the site PIs and designees. Consents and any other forms with identifiable subject information will be maintained in a separate locked file from the actual study data files, which will be identified only by subject number. All subjects will be informed regarding how HIPAA requirements may impact on their study records, and will sign a notification regarding this issue. All published data will be reported in a manner in which individual data for specific subjects are not identifiable.

The issue of “reproducible workflows and practices” is addressed in the originally submitted Multi-PI Plan (relevant text follows): “[name] and [name] will work closely to insure that the two study sites develop and implement identical procedures and training protocols, and that they acquire data in a coordinated and consistent fashion. Both [name] and [name] will be responsible for managing any potential missing data issues, to measure and correct for potential biases, and for administrative and fiscal oversight. Regular communication between the PIs via e-mail and telephone, as well as regularly scheduled in-person site visits will be used to coordinate the study sites. Similar coordination procedures have worked effectively in the PIs previous joint NIH-grant funded opioid blockade work (R01-MH071260, R01-DA031726, R01-DA037891).”

10.3 Quality Assurance

10.3.1 Training

The research assistants will be trained and daily supervised by the PIs. The PIs and RAs will meet at least weekly to review the week’s activities, protocol violations, questions and answers to ensure continued standardized administration of study protocol.

10.3.2 Quality Control Committee

There is no quality control committee.

10.3.3 Metrics

One person enters data, a second checks the data entry and compares to paper record. As a double check we will also check frequency and means of data to check for out of bound data entry errors.

10.3.4 Protocol Deviations

All protocol deviations will be noted in the protocol deviation log and participant’s chart. All protocol deviations (minor or major) will be reported to the corresponding site IRB through the PIs, and the deviation logs will be uploaded to the shared cloud-based document system. It is the policy of the IRB to be notified of any deviation from the protocol that results in an increase in risk or a decrease in potential benefit to participants. Consistent with IRB policies all minor deviations will be summarized and reported to the IRB at the continuing review. Major deviations will be

immediately reported to the IRB as specified by IRB procedures along with a corrective action plan to ensure that the deviation will not occur again. A “major deviation” is defined by the IRB as a deviation that impacts the safety of a subject or undermines the integrity of the study. In such a situation, the resulting IRB final response will be immediately forwarded to the NCCIH and IMC, along with the summary and corrective action plan submitted to the IRB.

A list of protocol deviations will be provided to the Independent Monitoring Committee (IMC) each quarter as part of the IMC progress report on January 15, April 15, July 15, and October 15. The more detailed semi-annual report will be submitted to the IMC on January 15 and July 15, and will include a list and summary of any major or minor deviations that occurred. As mentioned above, the IMC report prepared every 6 months will be signed by the members of the IMC and will be forwarded to the IRBs and NCCIH (reports will be provided more frequently on an ongoing basis if concerns are identified). All protocol deviations will be reported to NCCIH in the annual progress report and at site visits.

